6.1 Schedule of Evaluations

Measure	Pre-Course*	Course									3 Months	6 Months	
		1	2	3	4	5	6	7	8	9			
Feasibility Measures													
Attendance		X	X	X	X	X	X	X	X	X			
Attrition (Withdrawal)		X	X	X	X	X	X	X	X	X			
Audio Recording										X			
Screening Questionnaire (Demographics & PSS)	X												
Baseline Interview (JSS, Intent to Leave, ADQ, MBI, PSS, SCS, PROMIS)	X												
Weekly Questionnaire (PROMIS, Home Practice, Adverse Events)		X	X	X	X	X	X	X	X				
End-of-Program Interview (Acceptability Measure, JSS, Intent to Leave, ADQ, MBI, PSS, SCS, PROMIS, Adverse Events)									X	X			
3 Month & 6 Month Interview (JSS, Intent to Leave, ADQ, MBI, PSS, SCS, PROMIS, Adverse Events)											X	X	
Measures of Adverse Events and Safety Monitoring	Pre-Course*	Course									3 Months	6 Months	
		1	2	3	4	5	6	7	8	9			
PROMIS Depression Screen	X	X	X	X	X	X	X	X	X	X		X	X
Adverse Event Monitoring Form		X	X	X	X	X	X	X	X	X		X	X
Adverse Event Reporting Form					X				X			X	X
Nursing Home Level Data		2018			2019			2020					
Administrator Interview						X							
CMS NH Compare Website		X				X					X		
*Begins 2 weeks before onset of program													

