7.2 Adverse Events and Serious Adverse Events

Adverse event (AE): Any unfavorable and unintended change in physical or mental health status (i.e. new or worsening physical or mental health signs, symptoms, or disease) or loss of employment associated with participation in the study, regardless of whether it is considered related to the study.

A serious adverse event (SAE): Any AE that: results in death; is life threatening, or places the participant at immediate risk of death from the event as it occurred; requires or prolongs hospitalization; causes persistent or significant disability or incapacity; results in congenital anomalies or birth defects

Unanticipated problems (UPs): Involves risks to subjects or others to include, in general, any incident, experience, or outcome that meets all of the following criteria:

- Unexpected in terms of nature, severity, or frequency given (a) the research procedures that are described in the protocol-related documents, such as the IRB-approved research protocol and informed consent document; and (b) the characteristics of the subject population being studied;
- Related or possibly related to participation in the research (“possibly related” means there is a reasonable possibility that the incident, experience, or outcome may have been caused by the procedures involved in the research); and
- Suggests that the research places subjects or others at a greater risk of harm (including physical, psychological, economic, or social harm) than was previously known or recognized.

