7.3 Reporting Procedures

Given course content can bring up difficult emotions, study staff will monitor depressive symptoms weekly. Study staff will also ask participants to report any changes in their physical health that may be

related to their participation in the study, with the exception of transient discomfort during sitting practices. Examples of potentially relevant, although unlikely, physical health changes include: headaches, body or joint aches, or an injury occurring during mindfulness practice. These examples will be given to participants, with the caveat that they should err on the side of caution and over-reporting. Additionally, in order to monitor for participants' at risk of giving birth to a child with a birth defect, the intervention instructors will report to Principal Investigator and study staff if they learn of any pregnancy within their program participants.

In order to facilitate the reporting of potential AEs to study staff, the following procedures will be in place:

[1] During the 8-week intervention period, participants will be engaged in weekly group discussions about home practice, challenges to practice, and well-being. Any participant endorsing difficulties that the course facilitators feel are potentially beyond transient or typical will be approached privately to gather details.

[2] Participants will be given study staff contact information, including study phone and e-mail addresses. Participants will be encouraged to contact study staff in the event of psychological or potentially relevant physical health concerns.

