[3] At the beginning of each weekly session, and at 3 and 6-months post-intervention, we will administer a brief adverse event form, through the Weekly Questionnaire. On this form, we will collect data on any serious adverse events in the previous week, depressive symptoms via the validated 8-question PROMIS Depression Short Form and physical health changes possibly related to study participation. Regarding depressive symptoms monitoring, we will collect the PROMIS depression screen at baseline. For the purposes of this study, any participant whose PROMIS depression score moves from a lower category into the severe category (i.e. greater than or equal to a T-score of 70) will be flagged as a potential adverse event and will prompt follow up by the study team via a phone call by the study staff to gather details. Study staff will also notify the course instructors of the increased emotional distress so that extra support can be provided as needed.

The study team member receiving information from participants about a potential AE related to the study will complete an Adverse Event Form.

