7.4 Follow-up for Adverse Events

Data on AEs and UPs will be collected on an ongoing basis from study start to study completion.

General AE Procedures. The project manager or study staff will report all AEs to the PI immediately using the Adverse Event Reporting Form, after having gathered all necessary details (from the Weekly Questionnaire, as well as further communication with the participant if needed). The PI will determine the severity and the relatedness of the AE, and will confer with the SMC as needed. If the AE is serious and/or unexpected, possibly related to study participation, and suggests increased risk for participants, the procedures outlined below will also be followed.

AE reports will be collected by the project manager or study staff, summarized and de-identified. A summary report of all AEs to date will be sent to the PI and the SMC in both Phases at: 1) mid-intervention (4-week mark); 2) post-intervention (8-week mark); 3) post 3-month follow-up; 4) post 6-month follow-up.

Furthermore, all AEs will be summarized as part of the Data and Safety Monitoring Report submitted post-Phase 1 and post-Phase 2 to the SMC and NIA program officer. As per UNC IRB guidelines, all AEs will be reported to the UNC IRB during the yearly study review process.

Serious AE Procedures. The project manager or study staff will report all SAEs to the PI immediately using the Adverse Event Reporting Form, after having gathered all necessary details. For all deaths and for any SAE related or possibly related to study participation, the PI will send this report and any additional information, including corrective actions already taken, within 24 hours to the SMC chair, UNC IRB and NIA program officer. The PI will follow any additional course of action recommended by the UNC IRB, NIA, and/or SMC.

Unexpected and Related AEs/UPs with increased risk. All AEs that are deemed 1) unexpected; 2) possibly or probably related to study participation; and 3) suggests increased risk for study participants will be reported to the UNC IRB, NIA project officer, and the SMC chair within 48 hours of study team awareness of the event, using each organizations' respective reporting formats. In these reports, the PI will identify any corrective action planned or already undertaken. The PI will follow any additional course of action recommended by the UNC IRB, NIA, and/or SMC.

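### The automatic PROMIS depression trigger cannot fire for a participant who enters at T ≥ 70 and stays there, even if the score rises, and the visible protocol states no action for a severe baseline score

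*Protocol*

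**What the plan says.** Protocol section 7.3 explains why depression is watched: "Given course content can bring up difficult emotions, study staff will monitor depressive symptoms weekly". It also says "we will collect the PROMIS depression screen at baseline". A participant is flagged as a potential adverse event (AE) when the score "moves from a lower category into the severe category", with severe defined as a T-score of 70 or more. The flag leads to a phone call from study staff and a notice to the instructors so that they can give extra support.

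Section 7.2 defines an AE to include "new or worsening physical or mental health signs, symptoms, or disease", so worsening of an existing condition counts.

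Section 4.1 lists six inclusion criteria. None concerns depression, and the visible text lists no exclusion criteria.

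Section 7.3 gives two further routes. One is through the facilitators: "Any participant endorsing difficulties that the course facilitators feel are potentially beyond transient or typical will be approached privately to gather details". The other is through the participant: "Participants will be encouraged to contact study staff in the event of psychological or potentially relevant physical health concerns". Under section 7.4, "The project manager or study staff will report all AEs to the PI immediately using the Adverse Event Reporting Form".

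**The concern.** The trigger detects a crossing, not a level and not a rise. A participant already in the top category at entry has no lower category to move from. The people with the worst entry scores are thus the ones for whom the guaranteed call and instructor notice are unavailable, unless they first improve and then relapse.

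This matters on the protocol's own reasoning. Weekly monitoring exists because the course may stir up distress, and section 8 anticipates that some participants may have mental health needs that went unmet before the study. The AE summaries also go to the Safety Monitoring Committee, so worsening that nobody recognises would not reach its review.

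A second, smaller point is that section 7.3 does not say which assessment a move is judged against. The sentence just before the rule introduces the baseline screen, which hints at baseline. The plain words can equally be read from one assessment to the next.

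**Working it through.** The plan gives no figure to reproduce, so this is a check of the rule's logic.

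**Inputs.** The cut is T ≥ 70, with no higher category stated (section 7.3). PROMIS is collected at baseline, at each weekly session, at end of program, and at 3 and 6 months (sections 6.1 and 6.2.3).

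**Post-baseline screens.**
- 8-week course: 8 weekly + 1 end of program + 2 follow-up = 11.
- 6-week course: 6 weekly + 1 + 2 = 9.

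**The rule in both readings.** Against the previous assessment, it fires if some score is ≥ 70 and the one before it was < 70. Against baseline, it fires if baseline was < 70 and some later score is ≥ 70. If every score is ≥ 70, neither condition can be met. Enumeration agrees: over all paths of four assessments with integer T-scores from 70 to 81 (the upper limit is an assumption), there are 12⁴ = 20,736 paths, and the rule fires in 0 of them under either reading.

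**Illustrative paths (assumed scores).**

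| T-scores | Fires against previous | Fires against baseline |
|---|---|---|
| 71, 71, 71 | no | no |
| 70, 75, 80 | no | no |
| 72, 68, 72 | yes | no |
| 65, 69, 70 | yes | yes |
| 50, 60, 69 | no | no |

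A 1-point rise from 69 to 70 brings a call; a 5-point rise from 70 to 75 does not. The third row shows that the unstated reference decides whether a relapse is flagged.

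**How many participants.** The documents give no prevalence of T ≥ 70 at baseline. For scale only, assume a prevalence p and independent participants. The planned total is 3 × 15 = 45 and the maximum is 3 × 20 = 60. The expected number is n × p, and the chance of at least one is 1 − (1 − p)ⁿ.

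| Assumed p | n = 45: expected; chance of ≥ 1 | n = 60: expected; chance of ≥ 1 |
|---|---|---|
| 1% | 0.45; 36% | 0.6; 45% |
| 2% | 0.9; 60% | 1.2; 70% |
| 5% | 2.25; 90% | 3.0; 95% |
| 10% | 4.5; 99% | 6.0; >99% |

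These are chances that a participant enters at T ≥ 70. They are not chances that such a participant stays there, worsens or is missed.

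**The case against.** The strongest reply is that the trigger is one part of a wider safety net. Study staff hold the baseline interview one-on-one. Staff also conduct the End-of-Program, 3-month and 6-month interviews, all of which include PROMIS and adverse events. Absentees are given the weekly questionnaire by phone. Facilitators approach anyone whose difficulties seem out of the ordinary, and participants can contact staff themselves. Whoever learns of a potential study-related AE must complete a form, and all AEs go to the principal investigator.

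All of this stands. A reader might infer that a severe entrant has no safety cover, or that worsening would go unnoticed; the documents support neither. Once worsening is recognised as an AE, reporting it is a duty. What remains is that recognition by these routes depends on judgement or disclosure. As section 7.3 describes the weekly form, PROMIS is its only item on non-serious mental health change, and the one stated rule for acting on PROMIS leaves this group out.

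A reader might also infer that no plan exists for a severe baseline score. That goes too far, because the forms and appendices are not shown and could contain one.

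The contrast between 69 to 70 and 70 to 75 is partly how any cut-off behaves: a rise from 50 to 69 is not flagged either. This is fair. The illustration shows where the rule is silent, not that 70 is the wrong cut. Nor is a steady severe score an AE under section 7.2; only worsening is.

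**Conclusion.** The gap is real and narrow. For a participant at T ≥ 70 throughout, the automatic trigger fires at 0 of 11 post-baseline screens (8-week course) or 0 of 9 (6-week course), although a rise within the severe range could be worsening that section 7.2 counts as an AE. This follows from the wording alone and needs no assumed figure. That no action is stated for a severe baseline score holds for the visible text only.

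The number of participants affected, and the chance that worsening is overlooked, cannot be estimated from the documents. The unstated reference for a move is an ambiguity, not a demonstrated error. No efficacy result depends on any of this. It is a modest improvement to a safety procedure, worth considering because it is cheap.

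**What to change.** Amend section 7.3 as follows.

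1. Staff make a welfare call to any participant with baseline T ≥ 70. It is not recorded as an AE, and instructors are told only if the participant agrees.
2. Keep the existing trigger, and state that a move is judged against the previous assessment as well as baseline. Baseline alone would lose a relapse such as 72, 60, 72, which the present words can flag.
3. Also flag as a potential AE, with the existing call and instructor notice, any later T ≥ 70 that is higher than the participant's own severe baseline. The sponsor may set a small margin to avoid calls for trivial fluctuation.

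On the assumed paths, 71, 71, 71 then brings the welfare call only; 70, 75, 80 brings that call and flags at 75 and 80; 72, 60, 72 brings that call and a flag at the relapse. A severe entrant who improves within the severe range and then worsens without passing baseline would still not be flagged, so the other routes stay necessary.

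**Cost.** The scores are already collected and the staff are in place. For a severe entrant the most calls possible are 1 + 11 = 12 (8-week course) or 1 + 9 = 10 (6-week course), reached only if every later score exceeds baseline. There is also some sharing of sensitive scores. Section 7 names breach of confidentiality as a study risk and section 9.1 collects the weekly questionnaires confidentially, which is why item 1 asks for agreement first.

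A remark in section 4.1 suggests that the trial is complete. If so, apply the rule to the stored scores, report any cases with the AE summary, and use the rule in the planned randomized trial. The SAP gives PROMIS a range of 8–40, so stored totals on that range must be put on the T scale before the cut is applied.

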7.4 Follow-up for Adverse Events

Data on AEs and UPs will be collected on an ongoing basis from study start to study completion.

General AE Procedures. The project manager or study staff will report all AEs to the PI immediately using the Adverse Event Reporting Form, after having gathered all necessary details (from the Weekly Questionnaire, as well as further communication with the participant if needed). The PI will determine the severity and the relatedness of the AE, and will confer with the SMC as needed. If the AE is serious and/or unexpected, possibly related to study participation, and suggests increased risk for participants, the procedures outlined below will also be followed.

AE reports will be collected by the project manager or study staff, summarized and de-identified. A summary report of all AEs to date will be sent to the PI and the SMC in both Phases at: 1) mid-intervention (4-week mark); 2) post-intervention (8-week mark); 3) post 3-month follow-up; 4) post 6-month follow-up.

Furthermore, all AEs will be summarized as part of the Data and Safety Monitoring Report submitted post-Phase 1 and post-Phase 2 to the SMC and NIA program officer. As per UNC IRB guidelines, all AEs will be reported to the UNC IRB during the yearly study review process.

Serious AE Procedures. The project manager or study staff will report all SAEs to the PI immediately using the Adverse Event Reporting Form, after having gathered all necessary details. For all deaths and for any SAE related or possibly related to study participation, the PI will send this report and any additional information, including corrective actions already taken, within 24 hours to the SMC chair, UNC IRB and NIA program officer. The PI will follow any additional course of action recommended by the UNC IRB, NIA, and/or SMC.

Unexpected and Related AEs/UPs with increased risk. All AEs that are deemed 1) unexpected; 2) possibly or probably related to study participation; and 3) suggests increased risk for study participants will be reported to the UNC IRB, NIA project officer, and the SMC chair within 48 hours of study team awareness of the event, using each organizations' respective reporting formats. In these reports, the PI will identify any corrective action planned or already undertaken. The PI will follow any additional course of action recommended by the UNC IRB, NIA, and/or SMC.

The SMC will meet in person (or virtually for long-distance members as needed) at least 3 times throughout the study to review the Data and Safety Monitoring Report: 1) prior to first enrollment; 2) after completion of the field test (Phase 1) using the standardized intervention; 3) after completion of the refined intervention (Phase 2).

Additional meetings (ad-hoc) will occur as requested by the PI for review of unexpected adverse events or any SAEs that occur. Any recommended changes by the SMC will be submitted to the UNC IRB for approval.

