8 INTERVENTION DISCONTINUATION

We will prepare interim analyses to evaluate the safety of the intervention after Phase 1 and again after Phase 2. One of the tasks of the Safety Monitoring Committee (SMC) will be to review preliminary data from the study and make a recommendation RE whether or not the study should continue. The following are the reasons we propose for discontinuing the study early:

- The occurrence of a serious adverse event, possibly or definitely related to the study protocol, occurring in any participant. In this study, it would include serious psychological distress causing death, suicide attempt, or hospitalization.
- Severe adverse events, possibly or definitely related to the study protocol, occurring in 3 or more participants. In this study, this would include participants who withdrew from the study due to new psychological symptoms or who were hospitalized for mental health treatment. Given the high-stress nature of the participants jobs and lives, and given MSC involves prompting participants to become aware of and attend to their own needs, it is possible that study participation prompts mental health care that had been needed previously, but was perhaps ignored or not prioritized. Thus, severe cases will be examined carefully by the PI and SMC to determine if the cases warrant study discontinuation.
- Interim analyses will provide summary data related to the above bullets and study staff will make these data available to the SMC at least 2 weeks before meeting, or within 24 hours

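### The PI's relatedness rating decides whether a non-fatal SAE reaches the safety committee at once or only in a later periodic summary

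*Protocol*

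**What the plan says.** Protocol section 7.4 gives the causality judgement to the PI: "The PI will determine the severity and the relatedness of the AE, and will confer with the SMC as needed". Two expedited routes follow from that judgement.

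- **24 hours.** "For all deaths and for any SAE related or possibly related to study participation, the PI will send this report", and it goes "within 24 hours to the SMC chair, UNC IRB and NIA program officer".
- **48 hours.** This route covers "All AEs that are deemed 1) unexpected; 2) possibly or probably related to study participation; and 3) suggests increased risk" for participants. All three conditions must be met.

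There is also a routine route that does not depend on relatedness: "A summary report of all AEs to date will be sent to the PI and the SMC in both Phases at" four times, namely "mid-intervention (4-week mark); 2) post-intervention (8-week mark); 3) post 3-month follow-up; 4) post 6-month follow-up". Section 7.4 further sends all AEs to the SMC and the NIA program officer in the Data and Safety Monitoring Report after each Phase, and to the IRB yearly. The AE definition in section 7.2 includes events considered unrelated.

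On meetings, section 7.4 schedules three for the SMC (before first enrolment and after each Phase) and adds: "Additional meetings (ad-hoc) will occur as requested by the PI for review of unexpected adverse events or any SAEs that occur".

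The first discontinuation reason in section 8 is "The occurrence of a serious adverse event, possibly or definitely related to the study protocol, occurring in any participant". The second reason, severe events in three or more participants, carries the same relatedness condition. Section 8 asks the SMC to recommend whether the study should continue.

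**The concern.** One person's rating does two jobs. It fixes how fast the SMC hears of a non-fatal SAE, and it fixes whether that event counts toward a discontinuation reason that a single event can meet. The documents provide no second causality rating, and the PI need not consult the SMC before rating an event unrelated.

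Attribution is also hard for the events that matter most here. Section 8 itself notes that taking part may lead someone to seek mental health care that was needed before the study. A psychiatric admission could reasonably be rated either way. If it is rated unrelated, the committee asked to advise on continuation learns of it on a schedule of weeks to months, and could miss the chance to disagree while that home's course is still running.

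**Working it through.** No statistical figure in the plan bears on this point, so the check traces the text and then does simple date arithmetic.

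**Route of a non-fatal SAE, by the PI's rating**

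| Step | Rated possibly related | Rated unrelated |
|---|---|---|
| 24-hour report (7.4) | Yes | No |
| 48-hour report (7.4) | If also unexpected and suggesting increased risk | No |
| Periodic all-AE summary to SMC (7.4) | Yes | Yes |
| Post-Phase report to SMC (7.4) | Yes | Yes |
| Ad-hoc SMC meeting (7.4) | At the PI's request | At the PI's request |
| Counts toward first reason (8) | Yes | No |

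A death goes to the SMC chair within 24 hours under either rating.

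**Longest wait for the next scheduled summary**

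Inputs: summary times from section 7.4; course lengths of 8 weeks (Nursing Home 1) and 6 weeks (Nursing Homes 2 and 3) from section 5.1; follow-up interviews within 2 weeks either side of the 3- and 6-month marks from section 9.1. Assumptions: 3 months is 13 weeks, the 4- and 8-week marks are read literally for both course lengths, and each follow-up summary is issued when its interviews are done. Formula: longest wait = time of next summary − time of previous summary.

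- From the start to week 4, and from week 4 to week 8: 4 − 0 = 4 weeks and 8 − 4 = 4 weeks.
- Week 8 to the 3-month summary, 8-week course: (8 + 13) − 8 = 13 weeks, or 15 if the interview is 2 weeks late.
- Week 8 to the 3-month summary, 6-week course: (6 + 13) − 8 = 11 weeks, or 13 if 2 weeks late.
- The 3-month to the 6-month summary: 13 weeks, or 13 + 2 + 2 = 17 if the first is 2 weeks early and the second 2 weeks late.

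These are longest waits. An event just before a summary is reported almost at once.

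**Can a scheduled summary prompt action before sessions end?** An event in weeks 0 to 4 is summarised at week 4, with sessions remaining. An event after week 4 is next summarised post-intervention, when that home's sessions are over. That covers 4 of 8 weeks (half) of the longer course and 2 of 6 weeks (a third) of the shorter one. The follow-up waits of 11 to 17 weeks all fall after the home's course has ended.

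**Added reports if every SAE were expedited**

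Inputs: 45 CNAs (15 in Aim 1 and 30 in Aim 2) and 8 months per participant, from sections 3 and 5.1. The documents give no SAE rate; 5–10% of CNAs per year with an SAE is an assumption.

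- 45 × 8/12 × 0.05 = 1.5
- 45 × 8/12 × 0.10 = 3.0

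These are all SAEs. Those already expedited add nothing, so 1.5 to 3 is the ceiling at the goal of 45. At the cap of 20 per home (60 CNAs) it would be 60 × 8/12 × 0.05 = 2 to 60 × 8/12 × 0.10 = 4.

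**The case against.** The strongest reply is that the SMC is not kept in the dark. It receives all AEs, whatever their rating, four times per Phase and again in the post-Phase report. It can question a rating when it sees one. Deaths bypass the rating, and the threshold for the 24-hour report is low, since possible relatedness is enough. Ad-hoc meetings may cover any SAE, section 8 has the PI and SMC examine severe cases together, and an SMC charter outside these documents might let the chair convene a meeting.

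Most of this stands, and it rules out two stronger readings. A reader might infer that the PI's call decides whether a discontinuation reason is ever considered. The all-AE summaries and post-Phase reports do not support that. A reader might also infer that a delay of three months runs while sessions continue. The long gaps follow the end of that home's course, and the documents give no calendar showing that another home's sessions would overlap them.

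What the reply does not remove is the delay. No SMC meeting is tied to the periodic summaries, and nothing says that they carry case-level detail or that the SMC re-rates relatedness. The joint review of severe cases sits under a reason that already requires relatedness. The interim data in section 8 are tied to those same reasons.

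Two further points are fair. Sections 7.4 and 8 do not contradict each other, so this is a design choice. And section 4.1 refers to completion of the trial, so new wording cannot change reporting that has already happened.

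**Conclusion.** The point holds as a matter of timing and of who judges. The PI's rating, with SMC input only at the PI's discretion, controls whether a non-fatal SAE gets expedited SMC review and whether it counts toward the single-event reason. If the event is rated unrelated, the longest wait for the SMC is about 4 weeks during the course and about 11 to 17 weeks in follow-up, against 24 hours if it is rated possibly related. These figures rest on 13-week quarters and on a literal reading of the summary times.

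The documents give no basis for estimating how often the PI would misjudge relatedness, and the point does not need such an estimate. Severity is low: this is a cheap, optional improvement.

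**What to change.** In the Serious AE paragraph of section 7.4, send every SAE to the SMC chair on the existing 24-hour clock, whatever the PI's relatedness rating. Show the PI's rating on the report so that the chair can record disagreement. In the paragraph of 7.4 on ad-hoc meetings, state that the SMC chair as well as the PI may call one. Leave the discontinuation reasons in section 8 as they are.

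The cost is two wording changes and, on the assumed SAE rate, at most about 1.5 to 3 extra reports to an existing committee at the planned 45 participants, with no new staff. As this trial appears to be finished, the wording is mainly for the randomised trial that section 3 anticipates. For this study, the chair could still be asked to look at any SAE that was rated unrelated.
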